## Background

Nausea and vomiting after surgery (PONV) is a common side effect of the surgical procedure, general anesthesia and opioid use occurring in about one third of patients. In addition to being very unpleasant for patients, it is associated with longer recovery room stays and increased costs.[1] Specific prophylactic interventions may be applied during general anesthesia with the aim to prevent PONV in individual patients. These interventions mainly consist of administering one or more prophylactic drugs either at the start or the end of the procedure, and/or selecting a different type of anesthetic - i.e. total intravenous anesthesia rather than inhalational anesthesia. The efficacy of these interventions have been extensively studied in several clinical trials and meta-analyses.[2,3]

Current national guidelines as well as departmental guidelines recommend that patients receive prophylactic interventions for PONV according to their risk of PONV as predicted by a formal risk score.[1] A risk score predicts the PONV risk for each individual patient (Tables 1 and 2), based on specific characteristics of that patient and the scheduled procedure. However, in a busy operating room where the anesthesia provider performs multiple patient care tasks, closely following the recommendations to minimize the risk of PONV is often difficult.[4,5]

A clinical decision support system (CDSS) may help anesthesia providers to adhere to best practices for PONV prevention. Such a CDSS automatically calculates the risk of PONV for an individual patient and presents this predicted risk to the anesthesia provider on the computer screen that is being used by the anesthesia team for record keeping. In recent studies, such decision support systems have been demonstrated to improve adherence to PONV guidelines, especially when a recommendation on the number of interventions is added to the predicted risk.[6–8] Despite that improvement, there was still quite some room for improvement of the adherence to PONV guidelines in these studies.

Current literature on decisions support systems suggests that the design may have a great influence on what impact a CDSS has on medical decision making.[9] However, we are still only beginning to understand which CDSS design features will have the largest impact on the behavior of healthcare providers. The context of the clinical problem may be an important factor in what design for a decision support tool is the most appropriate.[5] The proposed study aims to improve the adherence to PONV guidelines by implementing multiple decision support elements with different design features.

## Research question and hypotheses

### Research question

Does the adherence to the recommendations of a clinical decision support system for postoperative nausea and vomiting depend on the proximity of the advice to specific decisions?

### Hypotheses

The research question will be addressed in this study by testing the following hypotheses:

1. An automated recommendation on PONV prophylaxis that is based on a patient-specific PONV risk that is sent by email to individual anesthesia providers the day before the scheduled procedure increases the adherence to PONV guidelines.

2. An automated recommendation on PONV prophylaxis that is based on a patient-specific PONV risk that is presented at the start of anesthesia increases the adherence to PONV guidelines (and has an added value to the automated email recommendation).

## Study Design and Participants

### Study design

The time series consists of three phases. The first phase is the preintervention phase – i.e. before the decision support has been implemented. The second phase is the first intervention phase in which the email with recommendations is being sent (Figure 1). The third phase is the second intervention phase in which the real time decision support guidance (Figure 2) is being displayed along with the email intervention.

### Study population

All adult patients (18 years and older) that are scheduled for an elective surgical procedure under general anesthesia within the study period will be considered eligible. We will exclude patients undergoing emergency surgery, and patients who will not go to the PACU to recover (i.e. patients that are transferred directly to the Intensive Care Unit or die intraoperatively). Procedures that only require a sedative level of anesthesia will be excluded from the analysis.

[figure not shown]

Figure 1. Screenshot example of email recommendations.

[figure not shown]

Figure 2. A screenshot mockup of the real-time decision support within our perioperative information management system.

Table 1 - Apfel's simplified risk score

Factor	Risk Score
Gender – Female	1
History of PONV/Motion sickness	1
Expected postoperative use of opioids	1
Non-smoker	1

Table 2 - Relation between predicted risks and recommendations

Number of PONV risk factors	Predicted PONV risk	Recommended number of interventions
0	0%	0
1	20%	1
2	40%	2
3	60%	3
4	80%	4

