## Outcome

### Primary outcome

The adherence to PONV guidelines will be used as the primary outcome. This is defined as an exact match between the recommended and applied numbers of interventions. Either a lower or a higher number of interventions will be considered as noncompliant to the guidelines. For the primary analysis the overall change in adherence as well as the added values of the different decision support elements to that adherence will be quantified. Medications with antiemetic properties will be considered prophylactic administrations, if they occur before the documented anesthesia stop time. We will consider scopolamine, dexamethasone, ondansetron, haloperidol, droperidol as prophylactic medications.

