### Statistical analysis plan

A two-sided alpha of 0.05 will be considered to be statistically significant. Continuous variables will be visually assessed for a normal distribution using histograms and QQ-plots. In descriptive statistics, parametric variables will be expressed as means with standard deviations, nonparametric variables will be expressed as medians with interquartile ranges, and discrete variables will be expressed as numbers with percentages. The primary analysis will be performed under the intention-to-treat principle. We will compare the incidence of the primary and secondary outcomes between the study groups utilizing analysis of variances to compare the means of multiple groups.

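### The unit of analysis is undefined: if a patient's repeat cases are included, plain ANOVA errors may be somewhat wrong, in either direction and probably by little

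*Combined protocol and SAP*

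**What the plan says.** The eligibility sentence in Study population is worded by patient: adults "that are scheduled for an elective surgical procedure under general anesthesia within the study period will be considered eligible". The exclusions cover emergency surgery, patients who do not recover in the PACU, and sedation-only cases. The last of these is worded by procedure: "Procedures that only require a sedative level of anesthesia will be excluded from the analysis". No section limits a patient to one case, and Data collection names the data warehouse without describing how multiple records of one patient are handled.

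The outcomes are per case. Of adherence, the Primary outcome section says: "This is defined as an exact match between the recommended and applied numbers of interventions". Drugs count if given before the recorded end of that anesthetic. Secondary outcomes counts PONV within a PACU stay.

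On design and analysis, Study design says: "The time series consists of three phases". The Statistical analysis plan says: "A two-sided alpha of 0.05 will be considered to be statistically significant". It then compares the groups "utilizing analysis of variances to compare the means of multiple groups". It has no repeated-measures, clustering or robust-variance term.

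**The concern.** A patient may have two or more elective procedures during the study, in one phase or in different phases. With outcomes scored per anesthetic and no rule on repeats, the most likely reading in practice is one row per anesthetic, each treated as independent by the ANOVA.

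The plan itself gives a reason to expect dependence. Table 1 scores "History of PONV/Motion sickness" as a predictor of PONV, so an earlier outcome is taken to inform a later one. Sex does not change between a patient's procedures, and smoking status usually does not. Part of the recommended number of interventions therefore carries over as well.

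Positive correlation within a phase makes the ANOVA standard error of a phase mean too small. Positive correlation across two compared phases makes the standard error of their difference too large. In either case the test does not run at its stated 0.05 level. Leaving the unit open also lets the choice of cases be made after the data are seen.

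**Working it through.** The plan gives no sample size, expected adherence, repeat share or correlation, so there is no figure of its own to reproduce.

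**Inputs.** From the documents: two-sided alpha 0.05 and three phases. Assumed: the share of repeats, the within-patient correlation ρ, and equal phase sizes. The quantity checked is the difference between two phase means.

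**Repeats within a phase.** With m cases per patient, true variance / ANOVA variance = 1 + kρ, where k = Σm²/Σm − 1.

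- 10% of patients with two cases: k = (0.9 + 0.1×4)/(0.9 + 0.1×2) − 1 = 1.3/1.1 − 1 = 0.182.
- 20% of patients with two cases: k = (0.8 + 0.2×4)/(0.8 + 0.2×2) − 1 = 1.6/1.2 − 1 = 0.333.

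**Repeats across the two compared phases.** The ratio is 1 − wρ, where w is the share of each phase's *cases* that belong to patients with one case in each phase. A share of patients would have to be converted to a share of cases first.

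**Actual type I error** = 2[1 − Φ(1.96/√ratio)].

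| Setting | ρ | Variance ratio | True SE / ANOVA SE | Actual level |
|---|---|---|---|---|
| Within, 10% of patients | 0.05 | 1.009 | 1.005 | 5.1% |
| Within, 10% of patients | 0.2 | 1.036 | 1.018 | 5.4% |
| Within, 20% of patients | 0.05 | 1.017 | 1.008 | 5.2% |
| Within, 20% of patients | 0.5 | 1.167 | 1.080 | 7.0% |
| Across, 10% of cases | 0.2 | 0.980 | 0.990 | 4.8% |
| Across, 30% of cases | 0.5 | 0.850 | 0.922 | 3.4% |

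For ρ = 0.2-0.5, within-phase ratios of 1.036-1.167 mean that the ANOVA variance lies 3.5% (1 − 1/1.036) to 14.3% (1 − 1/1.167) below the true variance.

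**Both kinds together.** The ratio is 1 + kρ − wρ. With 18.2% of cases in within-phase pairs, another 10% in across-phase pairs and ρ = 0.2, it is 1 + 0.036 − 0.020 = 1.016, an actual level of about 5.2%. Equal shares would cancel.

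**Check on the three-phase ANOVA itself.** A simulation used binary outcomes, an assumed 1,500 cases per phase, an assumed 40% adherence and 6,000 runs (Monte Carlo SE about 0.003). Here f is the share of cases in pairs; in the across runs, each phase's paired cases were split between the other two phases.

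| f | ρ | Repeats within | Repeats across |
|---|---|---|---|
| 10% | 0.2 | 0.057 | 0.047 |
| 20% | 0.3 | 0.062 | 0.045 |
| 30% | 0.5 | 0.074 | 0.042 |

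The directions agree with the formulas, and the departures are modest unless repeats are both common and strongly correlated.

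**The case against.** The strongest objection is that the mechanism is weak where it matters most. Adherence is a match between what was recommended and what the provider did. A stable target does not make the match stable: one provider may meet it and the next may miss it. Nothing in the documents supports a within-patient correlation of 0.2-0.5 for adherence. At 0.05 the within-phase settings give only 5.1-5.2%. This stands. The argument from Table 1 applies to PONV, which is secondary.

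Clustering by provider is probably the larger dependence. Under an assumed 20 cases per provider per phase, an intraclass correlation of 0.02 and no provider overlap between phases, the variance ratio is 1 + 19×0.02 = 1.38, an SE ratio of 1.17. That is a separate issue, but one sentence can cover both. Clustering by provider alone would still miss a patient's cases under different providers.

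A reader might also infer three stronger things:

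- *Eligibility runs by procedure and repeats will enter as independent.* The eligibility sentence makes patients eligible, and only one exclusion is worded by procedure. That repeats enter as independent rows is a likely inference, not something the plan states.
- *The intervals are wrong.* That depends on a repeat share and a correlation which the documents do not give.
- *A few patients with many procedures inflate the error seriously.* Suppose 85% of patients have one case, 9% two, 3% three, 2% five and 1% eight, all within a phase. Then k = 2.62/1.30 − 1 = 1.015, and ρ = 0.2-0.5 gives 7.4-11.0%. This rests on 15% of patients having repeats, a mix with no support in the documents.

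**Conclusion.** The gap holds as one of specification, and it is minor. The plan defines no unit of analysis, scores outcomes per anesthetic or PACU stay, and names an ANOVA with no allowance for dependence. If repeats are included, a nominal 5% two-phase test could run anywhere from about 3.4% to 7.0% over the assumed ranges. Within-phase repeats push it up and across-phase repeats push it down. Because the two partly cancel, the net effect is probably small, and its direction cannot be settled from the documents. The concern is most plausible for PONV and weaker for the primary outcome. All sizes rest on assumed repeat shares and correlations, equal phases and at most two cases per patient; more cases per patient would enlarge the within-phase effect.

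**What to change.** Add to the Statistical analysis plan that the unit of analysis is the anesthetic case, that cases of one patient are linked by a patient identifier in the data extract, and that phase contrasts use standard errors clustered both by patient and by anesthesia provider (two-way) in place of plain ANOVA errors. Add one sensitivity analysis restricted to each patient's first eligible case in the study period.

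The cost is one or two sentences and an identifier in the extract. Intervals may become slightly wider, and the sensitivity analysis will have fewer cases.

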## Outcome

### Primary outcome

The adherence to PONV guidelines will be used as the primary outcome. This is defined as an exact match between the recommended and applied numbers of interventions. Either a lower or a higher number of interventions will be considered as noncompliant to the guidelines. For the primary analysis the overall change in adherence as well as the added values of the different decision support elements to that adherence will be quantified. Medications with antiemetic properties will be considered prophylactic administrations, if they occur before the documented anesthesia stop time. We will consider scopolamine, dexamethasone, ondansetron, haloperidol, droperidol as prophylactic medications.

### Secondary outcomes

The occurrence of PONV within the patient's PACU admission. PONV will be defined as the administration of rescue antiemetics. The list of rescue antiemetics is similar to the list of prophylactic interventions, excluding the pre-anesthesia interventions, but complemented by the use of promethazine and compazine. Other secondary process outcome variables are: the absolute number of prophylactic interventions applied and time to discharge readiness at the PACU.

### Data collection

We plan to use the Perioperative Data Warehouse (PDW), an IRB-approved data repository, as the data source to study the effects of the decision support on the application of prophylactic interventions for PONV and the occurrence of PONV within the PACU.

### Data safety monitoring

The principal investigator (PI) will be responsible for data safety and monitoring within the VUMC. Quality control will include regular data verification and protocol compliance checks. Protocol adherence at the VUMC will be monitored by the PI throughout the study. Events determined by the PI to be unanticipated problems involving risks to subjects will be reported by the PI to the VUMC IRB within 10 working days of the Investigator's knowledge of the problem.

### Statistical analysis plan

A two-sided alpha of 0.05 will be considered to be statistically significant. Continuous variables will be visually assessed for a normal distribution using histograms and QQ-plots. In descriptive statistics, parametric variables will be expressed as means with standard deviations, nonparametric variables will be expressed as medians with interquartile ranges, and discrete variables will be expressed as numbers with percentages. The primary analysis will be performed under the intention-to-treat principle. We will compare the incidence of the primary and secondary outcomes between the study groups utilizing analysis of variances to compare the means of multiple groups.

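### Sequential phases are compared without adjusting for the 0–4 risk score that sets the target in the primary outcome, so a change in score mix could read as a phase effect

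*Combined protocol and SAP*

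**What the plan says.** Under Study design, "The time series consists of three phases": a period "before the decision support has been implemented", then a period with the email, then a period with the email plus real-time guidance. No randomisation or concurrent control is described. Study population applies one eligibility rule throughout and has no device to balance case mix between phases.

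Table 2 sets the recommended number of interventions equal to the number of risk factors, 0 to 4, and gives a predicted PONV risk that rises by 20 percentage points per factor. The primary outcome is an "exact match between the recommended and applied numbers of interventions", and a mismatch in either direction fails: "Either a lower or a higher number of interventions will be considered as noncompliant to the guidelines".

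The comparative analysis is one sentence in the Statistical analysis plan: "We will compare the incidence of the primary and secondary outcomes between the study groups", by analysis of variance. No covariate, stratification, standardisation, time term or sensitivity analysis is named. The Primary outcome section says that the overall change and the contribution of each decision support element will be quantified, but gives no adjusted method.

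**The concern.** The score is more than a general prognostic factor here, because it fixes one of the two numbers that must agree for a patient to count as adherent. If providers tend to give a habitual number of drugs, the match rate depends on the score by construction. In the extreme case where everyone receives two drugs, adherence is simply the share of patients who score 2.

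Overall adherence in a phase therefore depends on both prescribing and the score mix. The two hypotheses concern provider behaviour, and an unadjusted contrast between calendar periods mixes the two sources. The error can go either way. If match rates are lower at scores 3–4, a shift towards scores 1–2 could pass for a benefit of the email or the real-time tool, and the opposite shift could hide one. If match rates are higher at scores 3–4, the signs reverse.

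By Table 2 the score also predicts PONV, so the secondary comparison of PONV, defined through rescue use in the PACU ("PONV will be defined as the administration of rescue antiemetics"), is open to the same problem.

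**Working it through.** The documents state no sample size, baseline adherence, score distribution or expected effect, so there is no planned figure to reproduce. All inputs below are assumed, except the score-to-recommendation rule and the 20-point risk step (Table 2) and the two-sided alpha of 0.05 (Statistical analysis plan).

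**Step 1: adherence in a phase.** Adherence = Σ over scores of (share at score × match rate at score). Match rates are held the same in every phase, so there is no true effect.

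- Assumed mix for scores 0–4: 5/20/35/30/10%.
- Assumed main match rates: 30/45/50/20/5%.
- Baseline: 0.05×30 + 0.20×45 + 0.35×50 + 0.30×20 + 0.10×5 = 34.5%.

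**Step 2: shift the mix in phase 3 only.** Move a fraction d of all patients from scores 1–2 to scores 3–4, split 20:35 and 30:10 within the pairs. The change in adherence is d × (mean match rate at scores 3–4 minus mean match rate at scores 1–2).

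- Main rates: scores 1–2 average (20×45 + 35×50)/55 = 48.2%; scores 3–4 average (30×20 + 10×5)/40 = 16.25%. The difference is −31.9 points.
- d = 5%: −1.6 points (34.5% to 32.9%). d = 10%: −3.2 points (34.5% to 31.3%). The reverse shift gives +1.6 and +3.2.

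**Step 3: vary the match rates.**

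| Assumed match rates, scores 0–4 | d = 5% | d = 10% |
|---|---|---|
| Two drugs for everyone (0/0/100/0/0%) | −3.2 | −6.4 |
| Main (30/45/50/20/5%) | −1.6 | −3.2 |
| Flatter (35/40/42/28/20%) | −0.8 | −1.5 |
| Equal at all scores | 0 | 0 |
| Rising with score (30/35/35/45/45%) | +0.5 | +1.0 |

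**Step 4: how often the planned test would reject.** Three-group F test, phases 1 and 2 at the baseline mix and phase 3 shifted, main match rates, no true effect. The first unadjusted column is the noncentral F approximation; the others are simulated, 20,000 studies per cell.

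| Shift | Patients per phase | Unadjusted, noncentral F | Unadjusted, simulated | Adjusted for categorical score, simulated |
|---|---|---|---|---|
| 5% | 1,000 | 11% | 11.5% | about 5% |
| 5% | 2,000 | 18% | 17.5% | about 5% |
| 5% | 5,000 | 40% | 39.1% | about 5% |
| 10% | 1,000 | 33% | 32.5% | about 5% |
| 10% | 2,000 | 59% | 59.3% | about 5% |
| 10% | 5,000 | 95% | 94.8% | about 5% |

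The adjusted model ranged from 4.8% to 5.3%, and its mean phase 3 estimate was 0.0 points. With no shift, both models gave 4.8–5.4%. With the flatter rates at 2,000 per phase, the unadjusted test rejects in 8% (d = 5%) and 17% (d = 10%). A two-phase comparison with the main rates at 2,000 per phase rejects in 19% and 57%.

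**Step 5: a second set of assumptions.** Here 10 points move from score 3 to score 2 by phase 3, half of that by phase 2, with 400 simulated studies per setting. At 1,000 and 5,000 per phase the unadjusted test rejects in 6.8% and 15.5% with mild variation in match rates (40/45/45/35/25%), and in 12.3% and 39.5% with moderate variation (30/45/50/30/10%). The adjusted test gives 3.8–6.0% in these four cells, within simulation error of about ±2 points.

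**Step 6: PONV.** The shift in Step 2 raises the mean score from 2.20 to 2.28 (d = 5%) or 2.36 (d = 10%). At 20 points per factor, 0.08 × 20 = 1.6 and 0.16 × 20 = 3.2 points. Treat these as a ceiling: recommended prophylaxis rises with the score, and the outcome is rescue use in the PACU. At one third of the Table 2 risk they become 0.5 and 1.1 points.

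**Step 7: precision.** R² = 1 − E[p(1−p)]/[P(1−P)], where p is the match rate at a score and P is overall adherence. It is 0.114 for the main rates (standard error about 6% smaller after adjustment) and 0.026 for the flatter rates (about 1% smaller). This is a minor gain; the case rests on bias.

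**The case against.** The strongest reply is that nothing in the documents suggests the mix will move. One eligibility rule covers the whole study period, and bias needs both a mix shift and match rates that vary by score. The larger illustrative shift is not small: it lifts the share at scores 3–4 from 40% to 50%. Holding that shift fixed while the sample grows is what drives rejection to 95%. This stands as a limit on size. The rejection rates show a mechanism and do not forecast what this study will find.

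Second, the plan lists the absolute number of prophylactic interventions as a secondary outcome, and that count does not depend on the recommended number. If everyone received two drugs, a flat count beside moving adherence would expose the artefact. This is a partial safeguard only. The count is itself compared without adjustment and can move with the mix wherever practice follows risk.

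Third, adjustment reaches only the measured score mix. Secular trend, other case-mix changes and provider clustering remain. If the tools change how risk factors are recorded, the recorded score is partly a result of the intervention, and conditioning on it could itself shift the estimate. This also stands. It is the reason to report the unadjusted result alongside, though that result is not immune either, because the recorded score sets the recommended number.

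**Conclusion.** The concern holds. Non-randomised consecutive phases are compared with no adjustment for a score that enters the primary outcome by definition, and no other section supplies the adjustment. Calling the design a time series does not help, because no time-series model is specified.

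That the adjustment is absent is certain; the size and direction of any bias are not. On assumed inputs, a 5–10% shift in score mix gives a spurious change of about 1 to 3 percentage points with flatter or main match rates, up to 6.4 points if everyone gets two drugs, zero if match rates are equal, and the opposite sign if they rise with the score. This should be corrected because the remedy is cheap and bears directly on how the primary result is read.

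**What to change.** In the Statistical analysis plan:

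- Include the number of risk factors (0–4, categorical) as a covariate in the primary adherence model and in the models for the secondary outcomes.
- Report phase effects standardised to the pooled score distribution, with the unadjusted results beside them.
- Tabulate the score distribution by phase, and adherence by score and phase. If the mix proves stable, the first table will show it.

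Two supporting statements would help: that the score is derived from the data warehouse by the same rule in all phases, including the preintervention phase; and how patients with a missing risk factor are handled, with missingness of each factor shown by phase.

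The cost is SAP wording, one covariate per model and a few short tables. The score must already be derived for every patient to define the primary outcome, so no new data are needed. There are two downsides. Adjustment will not correct a change in how risk factors are recorded, and the secondary outcomes, which do not otherwise need the score, would then need the missing-factor rule.

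### Adherence and PONV are yes/no outcomes, but the only method named is analysis of variance; no method is given for phase 3 versus phase 2, and the default pooled error can mis-size it

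*Combined protocol and SAP*

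**What the plan says.** The Primary outcome section scores each patient as adherent or not: "This is defined as an exact match between the recommended and applied numbers of interventions". It adds: "Either a lower or a higher number of interventions will be considered as noncompliant to the guidelines". So the outcome is yes/no. PONV, under Secondary outcomes, is also yes/no: "PONV will be defined as the administration of rescue antiemetics". The remaining secondary outcomes are a count and a time: "the absolute number of prophylactic interventions applied and time to discharge readiness at the PACU".

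The Study design section sets out three successive phases: before decision support, email only, and email plus real-time guidance. Hypothesis 2 asks whether the real-time guidance adds to the email. The Primary outcome section makes this part of the primary analysis, in which the "added values of the different decision support elements to that adherence will be quantified".

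On inference, the Statistical analysis plan says: "A two-sided alpha of 0.05 will be considered to be statistically significant". The one comparison it names is to "compare the incidence of the primary and secondary outcomes between the study groups utilizing analysis of variances". It specifies no pairwise contrast, error term, interval or model for a proportion.

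**The concern.** A yes/no outcome with incidence p has variance p(1-p), so a change in incidence between phases will generally change the variance too. Ordinary analysis of variance assumes one error variance for all groups.

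This matters little for the overall test, whose null hypothesis makes all three incidences, and therefore all three variances, equal. It can matter for phase 3 versus phase 2. The null there is that on-screen guidance adds nothing to the email, while phase 1 may well differ because the email worked, as hypothesis 1 expects. A contrast built on the pooled mean square then takes part of its error variance from a phase outside the comparison.

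At stake are the false-positive rate and the interval for the added value of on-screen guidance, which is one of the trial's two hypotheses.

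**Working it through.** **Inputs from the documents.** Two-sided alpha 0.05 (Statistical analysis plan); three phases (Study design); two yes/no outcomes (Outcome). The Background gives PONV in about one third of patients. That is a general figure, not a planned phase 1 rate under the rescue-antiemetic definition.

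**Inputs assumed.** All phase-specific incidences and phase sizes. The documents state none, and there is no planned power or sample-size figure to reproduce.

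**Formula.** Let phase 1 have incidence p1, let phases 2 and 3 share incidence p (the null for the on-screen element), and let the phase sizes be in the ratio k:1:1.

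- Pooled error: MSE = [k·p1(1-p1) + 2·p(1-p)] / (k+2)
- Ratio of pooled to correct standard error: R = sqrt(MSE / [p(1-p)])
- True size of a nominal 5% test: 2·[1 - Φ(1.96·R)]

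**Worked case: 20% then 40%, equal phases.** p1(1-p1) = 0.16 and p(1-p) = 0.24. MSE = (0.16 + 2×0.24)/3 = 0.2133. R = sqrt(0.2133/0.24) = 0.943. Size = 6.5%. With phase 1 five times larger, MSE = (5×0.16 + 2×0.24)/7 = 0.1829, R = 0.873 and size = 8.7%.

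| Outcome | Phase 1, then phases 2 and 3 | R, k=1 | Size, k=1 | R, k=5 | Size, k=5 |
|---|---|---|---|---|---|
| Adherence | 20%, 30% | 0.960 | 6.0% | 0.911 | 7.4% |
| Adherence | 20%, 40% | 0.943 | 6.5% | 0.873 | 8.7% |
| Adherence | 20%, 50% | 0.938 | 6.6% | 0.862 | 9.1% |
| Adherence | 40%, 50% | 0.993 | 5.2% | 0.986 | 5.3% |
| Adherence | 50%, 80% | 1.090 | 3.3% | 1.184 | 2.0% |
| Adherence | 25%, 80% | 1.028 | 4.4% | 1.060 | 3.8% |
| Adherence | 30%, 70% | 1.000 | 5.0% | 1.000 | 5.0% |
| PONV | 30%, 20% | 1.051 | 3.9% | 1.106 | 3.0% |

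More extreme assumptions go further. Adherence of 10% then 50% gives 8.2% with equal phases and 13.8% with k=4. PONV of one third then 15% gives 2.9% with equal phases.

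**Total sample size.** R contains only the incidences and the relative phase sizes, so adding cases in the same proportions leaves it unchanged.

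**Simulation (40,000 replicates, independent patients, mostly 1,000 per phase).** The pooled contrast rejected 6.4% of the time for 20% then 50%, 8.9% for the same rates with 4,000 cases in phase 1, and 3.3% for 50% then 80%. A two-proportion test using only phases 2 and 3 rejected 4.9% to 5.3% of the time in every scenario run.

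**Overall test.** With all phases at 30% and 1,000 cases each, the F test and the chi-square test both rejected 4.9% of the time. With all at 10% and 300 cases each, both rejected 5.0%.

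**The case against.** The strongest reply is that the plan never says the contrast will use the pooled mean square. It specifies no contrast at all, and the test it does name, the overall F test, is sound. Nor do the documents promise a 95% interval; they give only the alpha. All of this stands, so the mis-sizing is a conditional risk of the analysis-of-variance default, not a stated error. What remains is that the added value of each element must be quantified and the plan does not say how.

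The size of the effect rests on assumptions. With mid-range adherence and similar phase sizes it is small: 5.2% to 6.6% when phase 1 is at 20% to 40% and the later phases at 50%. The larger figures need a much larger phase 1 or extreme rates, and the documents support neither.

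A reader might infer that the contrast is wrong whenever phase 1 sits at a different level, or that it is too narrow from a low start and too wide from a middling one. Neither holds. The driver is p(1-p), which is symmetric about 50%: 30% then 70% is unaffected, 25% then 80% (a low start) is too wide, and 40% then 50% (a middling start) is slightly too narrow.

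It is also fair to say that logistic regression on phase alone gives the same estimated proportions and risk differences as analysis of variance. Only the standard error changes, so a robust standard error on a linear model would do as well.

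Finally, the plan calls the design a time series and does not settle whether the patient or a period is the unit. The working above takes the patient as the unit, which is how both outcomes are defined.

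**Conclusion.** The concern holds in limited form. For two yes/no outcomes the plan names only analysis of variance, and it gives no method for the phase 3 versus phase 2 effect that hypothesis 2 and the primary analysis require. If the default pooled error fills that gap, the test and any interval are mis-sized whenever phase 1's p(1-p) differs from that of phases 2 and 3.

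Under the main assumed values, the true size of a nominal 5% test is about 3.3% to 6.6% with equal phases and about 2% to 9% with phase 1 four to five times larger. These figures assume independent patients and equal incidence in phases 2 and 3. They illustrate the possible error and do not predict it for this trial.

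A reader might conclude that the primary analysis as a whole is invalid. The documents do not support that, since the overall three-phase comparison is unaffected. The change is worth making because it also supplies the missing contrast and costs almost nothing.

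**What to change.** In the Statistical analysis plan, for adherence and PONV, replace analysis of variance with a binomial model on phase (logistic, for example) or a linear model with robust standard errors. Prespecify risk differences for phase 2 versus 1 and phase 3 versus 2, each with unpooled or robust standard errors and a confidence interval.

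Keep mean-based methods for the number of interventions and for time to PACU discharge readiness, with robust standard errors, so that neither is left without a method.

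The cost is one SAP sentence and standard code, with no new data or patients. The change cures unequal variance only. The near-nominal sizes shown for the two-group test assume independent patients, and dependence between patients who share a provider or a period would need separate treatment.
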